6 DATA HANDLING

6.1 Visit Window

Unless otherwise specified, no time window for visit/timepoints will be needed for analyses.

6.2 Unscheduled Visits, Retest, Withdrawal Visit,

All listings will include retests and unscheduled visits, while for the description by visit in the tables, only the scheduled visits according to the protocol will be described.

Unscheduled visit and retest measurements will be used to provide a measurement for a baseline data or endpoint value (e.g. worst value), if appropriate according to their definition. These measurements will also be used to determine abnormal laboratory, vital signs values or ECG.

If a value requires a retest (for laboratory values, vital signs and ECG) the closest non-missing reliable value to the scheduled visit will be used in the summary tables.

An assessment will be considered reliable if it is performed without any technical problem and if the result is within the range of likely values.

Participants who have withdrawn early from the study will have their last assessment entered at the end of study/early withdrawal visit in the eCRF. There is no remapping required for end of study/early withdrawal visit.

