1.3 Schedule of Activities (SoA)

The schedule of activities during the study is summarised for all participants in [Table 1](#), except the PK/PD subset of 12 participants which is summarised in [Table 2](#).

If the Coronavirus Disease 2019 (COVID-19) pandemic prevents participants from coming to the site, participants can have their study visit assessments performed remotely as judged appropriate by the investigator. This must be discussed with the sponsor before being implemented. In such a case, the investigator will perform a telemedicine visit and will make every effort, where applicable, to contact the participant's general practitioner or specialist physician to ensure all important medical information and safety event(s) occurring since the last visit are collected. Guidance on how to collect protocol-planned assessments will be provided to the investigator in a separate document. Such document will be filed in the trial master file. Independent ethics committees (IECs)/institutional review boards (IRBs) will be notified of the changes as applicable locally. Of note, as the adapted visit deviates from the regular protocol plan, the changes will be recorded as protocol deviations related to COVID-19.

Table 1 Schedule of Activities for All Participants Except the Pharmacokinetic/Pharmacodynamic Subset

Procedure	Screening		Intervention Period						EoS/EW
	End of Week	Day	Week 4	Week 8	Week 12	Week 16	Week 20	Week 24	
Visit Window	-	-	±3 days	±3 days	±3 days	±3 days	±3 days	±3 days	
Informed consent	X								
Eligibility	X	X							
Demography	X								
Medical and surgical history	X								
Physical examination [f]	X	X [a]			X				X
MRI scan [g]	X								
Disease-specific medical history	X								
Prior disease-specific treatment	X								
Body weight	X								X
Vital signs	X	X [a]	X	X	X	X	X	X	
12-lead electrocardiogram[b]	X		X						X
ECOG Score	X								
Injection triptorelin 6M		X							
Blood samples for triptorelin PK		X [a]	X	X	X	X	X	X	
Blood sample for testosterone PD [h]	X	X [a, e]	X	X	X	X	X	X	
Blood samples for PSA [h]	X	X [a, e]			X				X
Blood samples [c] laboratory safety tests	X	X [a, e]							X
Local tolerance [d]		X							
Previous (excluding disease-specific) and concomitant medication	X	X	X	X	X	X	X	X	
Adverse events	X	X	X	X	X	X	X	X	

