3 OBJECTIVES AND ENDPOINTS

Table 4 Objectives and Endpoints

Objectives	Endpoints
Primary	

 To evaluate the efficacy of triptorelin pamoate 22.5 mg 6-month formulation in achieving castrate levels of testosterone To evaluate the efficacy of triptorelin pamoate 22.5 mg 6-month formulation in maintaining the castrate levels of serum testosterone 	
 Percentage of participants achieving castrate levels of serum testosterone (<50 ng/dL or 1.735 nmol/L) on Day 29 Percentage of participants maintaining the castrate levels from Week 8 to Week 24
Secondary	

 To assess the safety profile including local tolerability of triptorelin pamoate 22.5 mg 6-month formulation 	
 Incidence of TEAEs (including local tolerability) throughout the study i.e., up to Week 24 Change from baseline in clinical safety laboratory parameters (blood chemistry and haematology) at Week 24 Change from baseline in physical examination at Day 1, Week 12 and Week 24 Change from baseline in ECG at Week 4 and Week 24 Change from baseline in vital signs (blood pressure and heart rate) at each visit up to Week 24

 To demonstrate the effect of triptorelin pamoate 22.5 mg 6-month formulation on PSA response 	
 Percent change in PSA from baseline (prior to injection) at Week 12 and Week 24 (percent change in PSA is defined as the absolute value of difference between the PSA values at Week 12 and Week 24 and the baseline value divided by the baseline value)

 To assess the PK of triptorelin pamoate 22.5 mg 6-month formulation in a subset of 12 participants 	
 PK parameters for dosing interval up to 24 weeks: 
 t_{max} C_{max} AUC_{0-169} AUC_{last}

 To assess the PD of testosterone in a subset of 12 participants 	
 PD parameters for dosing interval up to 24 weeks: 
 t_{max} C_{max} t_{cast}

 To assess the PK of triptorelin pamoate 22.5 mg 6-month formulation for all participants 	
 Sparse plasma concentrations of triptorelin at pre-dose and post-dose at Weeks 4, 8, 12, 16, 20 and 24

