5.1 General Considerations

All statistical analyses will be performed using the Statistical Analysis System® software version 9.4 (or higher if available).

5.1.1 *Outputs Presentation*

5.1.1.1 *Tables Header*

Depending on the type of data, the summary tables will be presented as follows:

- For disposition, demographic and baseline data: by treatment group,
- For efficacy and safety data: by treatment group.

5.1.1.2 *Presentation of Treatment Group*

Tables, Figures and Listings (TFLs) will be displayed using the following treatment group label:
Triptorelin 6M

5.1.1.3 *Presentation of Visits / Timepoints*

Summaries by visit will be presented using visit number as collected in the Electronic Case Report Form (eCRF).

Visits in the TFLs will be presented as follows and in the following order:

Long Visit Name	Short Name
Screening	Scr
Baseline	Bsl
Day 1	D1
Day 2	D2
Day 3	D3
Day 5	D5
Day 8	D8
Day 15	D15
Day 22	D22
Week 4 Day 29	W4D29
Week 8 Day57	W8D57
Week 12 Day85	W12D85
Week 16 Day113	W16D113
Week 20 Day141	W20D141
End of Study/Early Withdrawal	EoS/EW

In the event a participant is enrolled, but does not receive study intervention, the participant will not remain in the study and EoS/EW assessment will not be performed.

5.1.2 *Descriptive Statistics*

All raw and derived variables will be listed and described using summary statistics. For categorical variables, summary statistics will be displayed using descriptive statistics by frequency count and percentages by category. The missing category will be presented if there is at least one missing category for at least one treatment group. Except otherwise specified, participants with missing data will be included in the calculation of percentages. For quantitative variables, summary statistics will be displayed using descriptive statistics by number of observations, mean, standard deviation (SD), median, minimum and maximum. Frequency and proportion of missing data will be displayed.

5.1.3 *Baseline Value*

Unless otherwise specified, baseline is defined as the last non-missing measurement taken prior to first Investigational Medicinal Product (IMP) administration (including unscheduled assessments).

5.1.4 *Reference Start Date and Study Day*

Reference start date is defined as the day of the first IMP administration.

The day of the first IMP administration will be Day 1. Study day will be calculated as:

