- If the grade is missing for a TEAE, it will be considered as missing in the summary tables;
- Summary by grade will be presented;
- If the causality is missing for a TEAE, it will be considered related in the summary tables;
- The non-serious TEAEs table should include a specific row “any non-serious TEAE above 5%”.

In addition, a listing with all AEs data will be listed by treatment group including non-TEAEs, Treatment-emergence status will be flagged in the listing.

Deaths, SAEs, and Other Significant Adverse Events

The following summaries will be provided:

- A summary of the number and percentage of participants reporting a SAE by treatment group, SOC and PT,
- A summary of the number and percentage of participants reporting a treatment emergent SAE by treatment group, SOC and PT,
- A summary of the number and percentage of participants reporting a treatment-related SAE by treatment group, SOC and PT,
- A summary of the number and percentage of participants reporting a SAE by treatment group, maximum CTCAE grade, SOC and PT,
- A summary of the number and percentage of participants reporting a SAE by treatment group, maximum causality, SOC and PT,
- A summary of the number and percentage of participants with TEAEs leading to discontinuation of study by treatment group, SOC and PT,
- A summary of the number and percentage of deaths (including SAEs with fatal outcome and deaths as PT) including primary reasons for death.

AEs of special interest is not applicable.

The following listings will be provided:

- A listing of all deaths that occurred during the study,
- A listing of all SAEs.
- A listing of TEAEs leading to discontinuation of study.

5.8.4 *Laboratory Data*

All laboratory data (Hematology and Clinical Chemistry) will be presented in the units of International System of Units (SI).

The following summaries will be provided:

- A summary of the actual and change from baseline in each laboratory parameter by treatment group and visit,
- A shift from baseline to each post-baseline timepoints of the number and percentage of participants experiencing low, normal or high values, by laboratory parameter,
- A shift from baseline to end of study according to Common Toxicity (CTC) grading system (Version 5.0 or higher),

For shift tables, the denominator should be the number of participants with both a baseline and a post-baseline assessment at a given timepoint.

In addition, the following listings are to be provided:

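### The SAP's single end-of-study/early-withdrawal row pools Day 169 with earlier withdrawal values, so the safety changes that the protocol sets at Week 24 are not shown cleanly (minor)

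*SAP*

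**What the plan says.** **Endpoints.** Protocol section 3 (Table 4) ties the secondary safety endpoints to named times. For laboratory tests it is "Change from baseline in clinical safety laboratory parameters (blood chemistry and haematology) at Week 24"; for ECG it is "Change from baseline in ECG at Week 4 and Week 24". Physical examination and vital signs also have Week 24 as their last timepoint.

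**Schedule.** Protocol 1.3 (Table 1) has one final column that serves both Day 169 and early withdrawal. The row "Blood samples [c] laboratory safety tests" is marked only at screening, on Day 1 before the injection, and in that final column. ECG has one further post-dose visit, at Week 4. Protocol 7.2 asks for an early discontinuation visit when a participant leaves.

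**Visit handling.** The visit list in SAP 5.1.1.3 runs from Week 20 Day 141 straight to a combined end-of-study/early-withdrawal (EoS/EW) row, and by-visit summaries follow the eCRF visit number. SAP 6.1 states: "Unless otherwise specified, no time window for visit/timepoints will be needed for analyses". Under SAP 6.2, participants who leave early "will have their last assessment entered at the end of study/early withdrawal visit in the eCRF", and then: "There is no remapping required for end of study/early withdrawal visit".

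**Tables.** SAP 5.8.4 plans "A summary of the actual and change from baseline in each laboratory parameter by treatment group and visit". SAP 5.8.5 to 5.8.7 use the same visit structure for vital signs, ECG and physical examination. All are based on the Safety Set, which keeps every dosed participant.

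**The concern.** The protocol asks for a change at a fixed time, whereas the SAP's written rule produces a change at the last visit, whenever that fell. Anyone looking for the protocol's Week 24 laboratory or ECG result will go to the last row of the table, because no other row can hold it. A man who withdraws in the second month contributes to that row on the same footing as a man seen on Day 169.

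What is at stake is the reading of descriptive safety tables. If a laboratory value or ECG interval drifts over the 24 weeks, early values pull the row away from the Week 24 mean, and the mean, SD and median do not show by how much. Two other tables share the row: the descriptive triptorelin concentrations (SAP 5.9.1), whose Population PK Analysis Set is not limited to completers, and PSA percent change (SAP 5.7.3.2). The PSA effect is not quantified. Many dropouts fall outside the FAS, but treatment failures who leave early stay in it.

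**Working it through.** **1. The plan's own figures.** Protocol 9.2 and SAP 2.3 give 165 evaluable participants, null 85%, two-sided 0.05, power 88.3% at a true 93%, and 195 enrolled for about 15% dropout.
- The smallest count r with P(X ≥ r | n = 165, p = 0.85) ≤ 0.025 is r = 150 (tail probability 0.0173). Power at 93% is 0.8832, which matches 88.3%.
- 165 / 0.85 = 194.1, rounded up to 195, which matches.
- Implied dropouts: 195 − 165 = 30.

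**2. Does the rule pool?**
- Where do early values go? Into the EoS/EW visit (SAP 6.2).
- Does a window take them out? No general one applies (SAP 6.1). Day 169 ± 3 days is stated only for the testosterone co-primary endpoint (SAP 5.7.2.1); 5.8.4 to 5.8.7 and 5.9.1 add none.
- Does the restriction of by-visit tables to scheduled visits (SAP 6.2) take them out? No. EoS/EW is itself a scheduled column in Protocol 1.3.
- Is there another Week 24 row? No.

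**3. Illustrative share of early values.** Suppose all 165 have a Day 169 value and k of the 30 dropouts are dosed and sampled at withdrawal. The early share is s = k / (165 + k). Attendance is an assumption, because the documents do not give it.

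| Dropouts dosed and sampled | k | s |
|---|---|---|
| All | 30 | 30/195 = 15.4% |
| Half | 15 | 15/180 = 8.3% |
| A quarter | 7.5 | 7.5/172.5 = 4.3% |
| None | 0 | 0% |

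Two facts lower the share: enrolled men who are never dosed have no EoS/EW assessment (Protocol 7.1), and men lost to follow-up may give none.

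**4. Why 15.4% is not a ceiling.** The FAS counts treatment failures without requiring a Day 169 value, and Protocol 7.2 withdraws participants with confirmed inadequate suppression. Such men can be among the 165. At 93% maintenance, expected failures are 0.07 × 165 = 11.55, about 12. If all were withdrawn early and sampled, and all 30 dropouts were sampled too, the share would be (30 + 12)/195 = 42/195 = 21.5%. That is the extreme at the planned rates. Protocol 7.2 requires two consecutive high values, so not every failure would be withdrawn.

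**5. Effect on a row mean.** Row mean = (1 − s) × Week 24 mean + s × early mean, so the shift is s × (early mean − Week 24 mean). With s from 0 to 0.154, or 0.215 at the extreme, the shift is that fraction of a difference the documents do not give. No bias figure follows.

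**The case against.** The strongest defence is that this is an openly labelled convention. The protocol's own schedule uses one final column, the SAP row names both end of study and early withdrawal, study day appears in the listings, and everything is descriptive. A last-on-study value is a legitimate safety summary, and the CTC-grade shift table in SAP 5.8.4 is worded to end of study, so pooling suits it. The ECG summaries in 5.8.6 are offered only as ones that might be appropriate. Table shells are separate and not available here, and PK parameters and population PK modelling have their own plans, so only the descriptive concentration table is touched.

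All of that stands, and it keeps the point minor. It does not close the gap. A label that names both sources still does not say which row answers a Week 24 endpoint, and listings let a reader find individual early values but do not correct the summary statistics.

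A reader might go further and infer that the castration-maintenance result is contaminated in the same way. The documents do not support that. SAP 5.7.2.1 ties Week 24 to Day 169 ± 3 days, handles dropouts through rules (b) and (c), and excludes men who discontinue before Week 8. SAP 4 does not repeat the window in the FAS definition, but nothing there equates an early sample with Day 169.

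**Conclusion.** The concern holds as a minor one. Followed as written, the SAP reports a blend of Day 169 and early-withdrawal values in the only row that can carry the protocol's Week 24 safety changes. Laboratory tests are the clearest case, because they have no other scheduled post-dose visit. ECG, vital signs and physical examination have earlier post-dose rows, and only their final row is affected.

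The early share is illustrative: 0% to 15.4% if the 165 all reach Day 169, and up to about 21.5% if every expected failure were also withdrawn early and sampled. These figures rest on the planned dropout, the planned 93% maintenance and assumed attendance at withdrawal visits. It would be tempting to read any of them as a bias in the safety results, but the documents give no difference between early and Week 24 changes, so the effect could be negligible. The co-primary estimates, the 88.3% power and the sample of 195 are unchanged.

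**What to change.** In SAP 5.1.1.3, replace the combined last row with two rows: Week 24 Day 169, and Early Withdrawal. In SAP 6.2, replace the no-remapping sentence with:

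> A final-visit assessment is summarised as Week 24/Day 169 unless the participant is recorded in the eCRF as having discontinued the study and the assessment was taken before Day 166; such assessments are summarised under Early Withdrawal. They remain in listings, worst-value, shift-to-end-of-study and last-on-study summaries, and in the testosterone failure and escape derivations as already defined.

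Day 166 is the lower edge of the existing visit window (169 − 3). The rule uses recorded discontinuation and not completion, because SAP 2.2 and SAP 4 define completing the study differently. A man who misses an interim visit but attends Day 169 therefore stays in the Week 24 row, as does a man seen late. SAP 4 and 5.7.2.1 need no rewording for this.

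The cost is a few sentences, one extra label and a derivation from dates and status already collected. The Week 24 descriptive rows lose a few values: about 165 of 195 remain at the planned dropout, or about 153 (165 − 12) if every expected failure were withdrawn early. No safety value is dropped from the report.

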7 DERIVED DATA (IF APPLICABLE)

Not applicable.

8 REFERENCES

Reference to ICH regulatory guidelines:

- ICH E3: Structure and Content of Clinical Study Reports
- ICH E6 (R2): Good Clinical Practice
- ICH E9: Statistical Principles for Clinical Trials
- ICH E9 (R1) Addendum: Estimands and Sensitivity Analysis in Clinical Trials

Reference to European Medicines Agency (EMA) or point to consider guidelines:

- Adjustment for baseline covariates in clinical trials
- Choice of a non-inferiority margin

- Clinical trials in small populations
- Data monitoring committees
- Investigation of subgroups in confirmatory clinical trials
- Missing data in confirmatory clinical trials
- Application with Meta Analyses, One pivotal study
- Multiplicity issues in clinical trials

Switching between superiority and non-inferiority

Reference to Food and Drug Administration (FDA) guidelines:

- Clinical Trial Endpoints for the Approval of Cancer Drugs and Biologics
- Multiple Endpoints in Clinical Trials

Reference to NMPA guidelines:

- Clinical trial data management and statistical analysis plan
- Submission of clinical trial data

Standard Ipsen SDTM user guide

Standard ADaMs user guide

Ipsen Global Style guide

Reference to statistical methods:

- [name] PhD, SI unit conversion guide. *The New England Journal of Medicine*, 1992

9 APPENDICES**A1. SAS Code****Sample code computing Clopper-Pearson 95%CI**

“efficacy” sample data*

Participant ID	ACHPPD (Achieve Testosterone at Day 29)	MAINPD (Maintain Testosterone from Week 8 to Week 24)
001	1	1
002	2	2
003	1	1
004	2	2
005	1	2
006	1	1
007	1	1

* This is just sample data for reference: 1 = Yes; 2 = No.

```
proc freq data=efficacy;
  table ACHPD / binomial;
  exact binomial;
run;
proc freq data=efficacy;
  table MAINPD / binomial;
  exact binomial;
run;
```

A2. Partial/Missing Date Convention

In all listings, missing or incomplete dates should be left as they have been recorded. However, for calculation / sorting / assignation based on dates, the following methods will be used:

- The most conservative approach will be systematically considered (i.e. if the onset date of an AE/concomitant medication is missing / partial, it is assumed to have occurred during the study treatment phase (i.e. a TEAE for AEs) except if the partial onset date or the stop date indicates differently).
- Where this is possible, the derivations based on a partial date will be presented as superior inequalities (i.e.: for an AE started in FEB2004 after the first IMP administration performed on 31JAN2004, the days since last dose will be “ ≥ 2 ”, similarly the duration of ongoing AEs or medication will be “ $\geq xx$ ” according to the start and last visit dates).

Algorithm for Prior/ Concomitant

Medication, non-drug therapies and surgical procedures start and stop dates will be compared to the date of the first IMP administration to allow classification as either Prior only, Prior and Concomitant, or Concomitant only.

In case of partial start and/or stop medication/ non-drug therapies/surgical procedures dates, imputation will be done to determine the classification:

- If a partial start date, the first day of the month will be imputed for missing day and January for missing month,
- If a partial stop date, the last day of the month will be imputed for missing days and December will be imputed for missing month.

In case incomplete start or stop date does not allow the classification, will be classified as concomitant.

Algorithm for TEAE

For deriving the TEAE flag the following process of temporary date imputation is done (for AE start date only assuming no AE end date are missing). The date imputation algorithm for incomplete adverse event start dates is described in Table 1. Classification of adverse event according to its treatment-emergent status is then done using the imputed date.

In the following table, all dates are presented using an YYYY-MM-DD format. As an example, suppose First IMP administration = 2002-08-11 and several AEs have incomplete start dates.

Table 1: Data imputation algorithm for AE start date

Description of incomplete date	Imputed numeric date	Example	
		Character date	Imputed date
Day is missing			
YYYY-MM < YYYY-MM of [First IMP admin.]	YYYY-MM-01	2002-07-XX	2002-07-01
YYYY-MM = YYYY-MM of [First IMP admin.]	Min ([First IMP admin.], AE end date)	2002-08-XX	Min (2002-08-11, AE end date)
YYYY-MM > YYYY-MM of [First IMP admin.]	YYYY-MM-01	2002-09-XX	2002-09-01
Day and month are missing			
YYYY < YYYY OF [First IMP admin.]	YYYY-01-01	2001-XX-XX	2001-01-01
YYYY = YYYY OF [First IMP admin.]	Min ([First IMP admin.], AE end date)	2002-XX-XX	Min (2002-08-11, AE end date)
YYYY > YYYY OF [First IMP admin.]	YYYY-01-01	2003-XX-XX	2003-01-01
Day, month, and year are missing			
XXXX-XX-XX	Min ([First IMP admin.], AE end date)		Min (2002-08-11, AE end date)

YYYY = non-missing year, MM = non-missing month, DD = non-missing day, XX = missing field.

If AE end date is partial, imputation could be done assuming the latest possible date (i.e. last day of month if day unknown, or 31st of December if day and month are unknown).

A3. Programming Convention for Outputs

All text fields must be left justified and numeric or numeric with some text specification (e.g.: not done, unknown, <4.5, ...) must be decimal justified.

The mean, median, and SD will be reported to one decimal place greater than the raw data recorded in the database. The minimum and maximum values will be reported with the same number of decimal places as the raw data recorded in the database. In general, the maximum number of decimal places reported should be four for any summary statistic.

Percentages will be presented to one decimal place. Percentages will not be presented for zero counts. Percentage will be calculated using n as denominator. The denominator n will be specified in a footnote for clarification if necessary. If sample sizes are small, the data displays will show the percentages, but in the CSR only frequency counts should be described.

P-values will be reported to four decimal places (e.g.: p=0.0037), after rounding. P-values which are less than 0.0001 will be presented as '<0.0001'.

Dates will be presented in the format [ddMmmyyyy] and times in the format [hh:mm].

A4. Listings Conventions

Any listings will contain at least the following data: participant identifier, age and gender. When dates are presented, the associated study days should be included. They should be sorted by treatment group then participant identifier. For multicentre studies, listings should be broken down by centre and treatment group.

A5. EudraCT Categories for Age

For EudraCT results summaries, in addition to quantitative descriptive statistics of age, demographic tables should include presentation of age using the following EudraCT categories (as applicable):

Adults (18-64 years)
From 65 to 84 years
85 years and over

A6. CTCAE V5.0 Grading for Laboratory Values

Grade is classified based on the numeric lab result criteria in CTCAE v5.0 grading. The clinical criteria or condition will not be used.

Analytic	CTCAE SOC	CTCAE Term	Grade 1	Grade 2	Grade 3	Grade 4	Grade 5
Hematology							
Hemoglobin	Blood and lymphatic system disorders	Anemia	<LLN - 100 g/L	<100 - 80 g/L	<80 - 65 g/L	< 65 g/L	-
Hemoglobin	Investigations	Hemoglobin increased	Increase in >0 - 2 gm/dL above ULN	Increase in >2 - 4 gm/dL above ULN	Increase in >4 gm/dL above ULN	-	-
Platelet count	Investigations	Platelet count decreased	<LLN - 75,000/mm ³ ; <LLN - 75.0 x 10 ⁹ /L	<75,000 -50,000/mm ³ ; <75.0 - 50.0 x 10 ⁹ /L	<50,000 - 25,000/mm ³ ; <50.0 - 25.0 x 10 ⁹ /L	<25,000/mm ³ ; <25.0 x 10 ⁹ /L	-
White blood cell count (total)	Investigations	White blood cell decreased	<LLN - 3000/mm ³ ; <LLN - 3.0 x 10 ⁹ /L	<3000 - 2000/mm ³ ; <3.0 - 2.0 x 10 ⁹ /L	<2000 - 1000/mm ³ ; <2.0 - 1.0 x 10 ⁹ /L	<1000/mm ³ ; <1.0 x 10 ⁹ /L	-
White blood cell count (total)	Blood and lymphatic system disorders	Leukocytosis	-	-	>100,000/mm ³ ; >100 Giga /L	-	-
Neutrophils (Abs)	Investigations	Neutrophil count decreased	<LLN - 1500/mm ³ ; <LLN - 1.5 x 10 ⁹ /L	<1500 - 1000/mm ³ ; <1.5 - 1.0 x 10 ⁹ /L	<1000 - 500/mm ³ ; <1.0 - 0.5 x 10 ⁹ /L	<500/mm ³ ; <0.5 x 10 ⁹ /L	-
Lymphocytes	Investigations	Lymphocyte count decreased	<LLN -800/mm ³ ; <LLN- 0.8 x 10 ⁹ /L	<800 - 500/mm ³ ; <0.8 - 0.5 x 10 ⁹ /L	<500 - 200/mm ³ ; <0.5 - 0.2 x 10 ⁹ /L	<200/mm ³ ; <0.2 x 10 ⁹ /L	-
Lymphocytes	Investigations	Lymphocyte count increased	-	>4000 - 20,000/mm ³ ; >4 - 20 Giga /L	>20,000/mm ³ ; >20 Giga /L	-	-
Eosinophilia (Abs)	Blood and lymphatic system disorders	Eosinophilia	>ULN	-	-	-	-
Biochemistry							
Creatinine	Investigations	Creatinine increased	>ULN - 1.5 x ULN	>1.5 - 3.0 x ULN	>3.0 - 6.0 x ULN	>6.0 x ULN	-
Glucose	Metabolism and nutrition disorders	Hyperglycemia	>ULN - 8.9 mmol/L	>8.9 - 13.9 mmol/L	>13.9 - 27.8 mmol/L	>27.8 mmol/L	-

CONFIDENTIAL

PROTOCOL: FINAL WITH AMENDMENT 3: VERSION 4.0, 08 MARCH 2024

PAGE 32/32

Analytic	CTCAE SOC	CTCAE Term	Grade 1	Grade 2	Grade 3	Grade 4	Grade 5
Glucose	Metabolism and nutrition disorders	Hypoglycemia	<LLN – 55 mg/dL; <LLN – 3.0 mmol/L	<55 – 40 mg/dL; <3.0 – 2.2 mmol/L	<40 – 30 mg/dL; <2.2 – 1.7 mmol/L	<30 mg/dL; <1.7 mmol/L	-
Total Bilirubin	Investigations	Blood bilirubin increased	>ULN – 1.5 x ULN	>1.5 – 3.0 x ULN	>3.0 – 10.0 x ULN	>10.0 x ULN	-
Total Bilirubin	Hepatobiliary disorders	Sinusoidal obstruction syndrome	-	>34.2 - 85.5 umol/L	>85.5 umol/L	-	-
Alanine Aminotransferase	Investigations	Alanine aminotransferase increased	>ULN – 3.0 x ULN	>3.0 – 5.0 x ULN	>5.0 – 20.0 x ULN	>20.0 x ULN	-
Aspartate Aminotransferase	Investigations	Aspartate aminotransferase increased	>ULN – 3.0 x ULN	>3.0 – 5.0 x ULN	>5.0 – 20.0 x ULN	>20.0 x ULN	-
Alkaline Phosphatase	Investigations	Alkaline phosphatase increased	>ULN – 2.5 x ULN	>2.5 – 5.0 x ULN	>5.0 – 20.0 x ULN	>20.0 x ULN	-
